STUDY PROTOCOL

Baropodometric parameters variation with body weight loss: a prospective cohort study

DATE: 11 January 2021

Scientific Background

Obesity is in one of the major public health problems of the 21st century and its prevalence has tripled in many European countries in the last decades (1). It is a strongly problem associated with a lower quality of life, as well as with the development of serious chronic metabolic, cardiac and circulatory pathologies and musculoskeletal disorders (2,3). Quantitative data showed that excessive body weight negatively effects on standing and walking (4,5).

Plantar pressure measurement is commonly used to determine specific loads on the plantar surface of the foot. There are many case studies that assess pressures of the normal foot and try to establish patterns of pathological pressures (6). The CoP represents the average of all the weight that is in contact with the surface of the floor and is expressed as the point where the vector of the vertical reaction forces of the soil is located (6,7).

In the literature it can be found how body weight influences on plantar pressure data and on the position of the CoP (8-10). Excesses of body weight has shown to have negative structural consequences in the feet and lower limbs (11-14). Obesity is also related with an anterior displacement of the CoP (15), since the instability in obese people, associated to weight increasing, seems to be determinant with CoP in an anterior position (16).

Computerized baropodometry is helpful for foot diseases diagnosis, foot function evaluation and to follow-up the treatment. It has been practiced to determine specific weight parameters in obese adults, among others (10,14). Nonetheless, there are not in the literature specific studies that have analyzed by computerized baropodometry how plantar pressures and CoP improve by decreasing body weight in obese adults.

Objective

The present research wanted to evaluate plantar pressures and antero – posterior CoP improvement by decreasing body weight in static and dynamic baropodometry data collection in obese adults.

Design

The design of the present research was based on and executed according to the STROBE reporting guideline. The study was approved by the Ethics Committee of Clinical Research of Aragón (CEICA) with number C.P.-C.I. PI17/0203. Participants voluntarily signed an informed consent. The study has been conducted in accordance with the Helsinki Principles.

Participants

The study would include overweight subjects between 18 and 65 years old, medical weight loss indicated, no lower limb or spine pathology that might affect normal gait, nor structural or functional deformities in the feet. Candidates who not comply inclusion criteria, or reported pain in their feet within the previous 6 months, or had any previous foot surgery would be excluded. Them would be recruited at one Endocrinology and Nutrition private clinic in Huesca, Spain.

Procedure

Participants would be rigorously evaluated by the same endocrine doctor and podiatrist at baseline (Session 1) and at the end of the study after weight loss intervention (Session 2), when each participant lost between 11-12% of its corporal weight. Therefore, we will obtain 2 weight related with the two sessions: Session 1 – Weight 1; Session 2 – Weight 2.

In order to achieve the propose weight loss, lifestyle modification would be applied (17): A specific very low-calorie diet (<800kcal/day), and 2 daily sessions of 15 minutes of anaerobic physical exercise depending on the capacity of the participants (18,19).

At Session 1 and Session 2, before and after weight loss intervention, participants would be subjected to a baropodometric examination (static and dynamic). It allows to quantitatively mapping pressures in each segment of the plantar surface (20,21). For the static, participants would be asked to stand in the center of the platform for 5 seconds, with their arms on either side of the body in a natural position looking straight ahead (22). To minimize individual's corporal fluctuations in static (as body weight oscillation and imbalance) the procedure would be applied 3 times per session (22). For the dynamic, participants would be asked to walk barefoot on the platform at their normal pace following the 3-step protocol, which requires landing on the platform on the third step of gait (23). To minimize corporal individual fluctuations in dynamic (as body weight oscillation, imbalance and changes in gait speed) the procedure would be applied 3 times per session (22). Both feet would be subdivided into 9 areas: heel, midfoot, 5 MTHs, the Hallux, 2-5 toes. Selection of the areas of the present study are based in the research of Hills et al. (11), who performed a complete study of the differences of pressures between obese and non-obese subjects.

Peak pressures of these areas in kg/cm² and the position of the CoP, were obtained using the Footwork® software (20). Peak pressure data were graphically exposed and related with the two weights for each patient.

Equipment

Participant's weight and height were measured during each session with an Año-Sayol scale and stadiometer, respectively (Año-Sayol SL, Barcelona, Spain).

Footwork® platform (AM3-IST®, France), was used for the baropodometric analysis (22, 24).

Statistical Analysis

An initial exploratory analysis of all clinical variables would be carried out. Continuous variables would be expressed as mean \pm standard deviation (SD), whereas qualitative variables would be expressed as frequencies and percentages. Continuous data would be checked for normality by Kolmogorov-Smirnov Test. Chi-Square Test would be applied to show the relationship between qualitative variables. To compare mean weights between two independent groups according to normality, Student's-T Test and ANOVA Test to "m" groups would be used. Differences between Session 1 and Session 2, would be performed using mean comparison methods, Wilcoxon when the variable does not follow normal distribution, and Student's T for related samples when there is normality. To quantify the difference between weight and plantar pressures and the CoP at Session 1 and Session 2 the "change percentage" would be calculated, which would be defined as the relative variation in percentage points between both sessions: Weight-Change % (WC%) = [(Weight at Session 2 – Weight at Session 1)/ Weight Session 1] x 100; Plantar-Pressure-Change % (PPC%) = [(Pressure at Session 2 – Pressure at Session 1)/ Pressure at Session 1] x 100; CoP-Change % = [(time CoP X+1 – time CoP X)/ time CoP X] x 100. The "change percentage" would be analyzed through Spearman correlation coefficient, according to normality.

The "improve" variable would be established in order to analyze the possible relationship between weight loss and the 9 pressure foot areas considered at Session 1

and Session 2 for both: static and dynamic baropodometry. Statistical significance level would be set at $p < 0.05$, confidence level set in the comparisons was 95%. The statistical analyses would be performed using the SPSS software 22.0 for Windows (SPSS Ibérica, Madrid, Spain).

REFERENCIAS

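### Follow-up is measured only at 11-12% weight loss, so the paired result covers only those who reach the target and a correlation with percentage weight change is uninformative

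*Combined protocol and SAP*

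**What the plan says.** The Procedure section defines two measurement occasions and no others: "Therefore, we will obtain 2 weight related with the two sessions: Session 1 – Weight 1; Session 2 – Weight 2". The second takes place "at the end of the study after weight loss intervention (Session 2), when each participant lost between 11-12% of its corporal weight". Plantar pressure and centre of pressure (CoP) are recorded on the same two occasions: "At Session 1 and Session 2, before and after weight loss intervention, participants would be subjected to a baropodometric examination (static and dynamic". The target is pursued by diet and exercise ("In order to achieve the propose weight loss, lifestyle modification would be applied"). The document gives no calendar time for Session 2, no maximum follow-up, no rule for a participant who does not reach the target, and no missing-data method.

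The Statistical Analysis section compares the sessions with paired tests ("Wilcoxon when the variable does not follow normal distribution, and Student's T for related samples when there is normality"). It then defines relative changes, including "Weight-Change % (WC%) = [(Weight at Session 2 – Weight at Session 1)/ Weight Session 1] x 100", with matching formulas for pressure (PPC%) and CoP. The change percentages "would be analyzed through Spearman correlation coefficient, according to normality". A further variable, labelled improve and not defined, is introduced "in order to analyze the possible relationship between weight loss and the 9 pressure foot areas considered at Session 1".

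**The concern.** Two consequences follow from making the second measurement conditional on the result of the intervention.

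**Who is in the paired analysis.** A paired test uses only people with both sessions. As written, these are the people who reached the target, a group selected on something that happens after baseline. The Objective refers to obese adults in general. Those who reach the target could differ from those who do not, for example in exercise capacity, which the Procedure section lets vary between participants.

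**What the correlation can show.** Correlating weight change with pressure change across participants requires that weight change differ between them. The trigger for Session 2 removes nearly all of that variation. A coefficient near zero would be the expected result even if pressure falls in step with weight, and it could easily be reported as evidence that the amount of weight lost does not matter.

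**Working it through.** The plan states no sample size, effect size, SD, dropout rate or follow-up time, so there is no figure of its own to reproduce. The one documented input is the 11-12% window. Everything marked *assumed* below is not in the document.

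**1. Spread of WC% inside the window**
- Range: 12 - 11 = 1 percentage point (1.0 kg for a 100 kg person).
- Uniform in the window: SD = 1/√12 = 0.289.
- Largest possible, half the participants at each end: SD = 0.50.

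**2. Expected correlation of WC% with PPC%**

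*Assumed*: PPC% = 1 × WC% + noise, noise SD 10-20 points. Then r = SD_w / √(SD_w² + noise²).

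| SD of WC% | Noise 10 | Noise 15 | Noise 20 |
|---|---|---|---|
| 0.289 (uniform) | 0.029 | 0.019 | 0.014 |
| 0.50 (maximum) | 0.050 | 0.033 | 0.025 |

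**3. Second route, by range restriction**

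r′ = r·u / √(1 - r² + r²u²), where u = window SD / unrestricted SD.
- *Assumed* unrestricted SD 5 points and r = 0.5. Uniform: u = 0.289/5 = 0.058, r′ = 0.033. Maximum spread: u = 0.10, r′ = 0.058.
- Over *assumed* unrestricted SDs of 3-6 points and r of 0.3-0.7, r′ is 0.015-0.094 (uniform) or 0.026-0.161 (maximum spread).
- Sample size for 80% power at two-sided 0.05 (two-sided is itself *assumed*): n = ((1.960 + 0.842)/atanh r)² + 3. For r = 0.5, n is 30. For r′ = 0.058 it is 2,361, and for r′ = 0.033 it is 7,070.

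**4. Simulation of the Spearman test** (3,000 runs per setting, slope 1, noise SD 10 or 15)

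With WC% uniform in the window, the rejection rate at n = 30, 60 and 100 is 4.8-5.5%, no better than the 5% significance level.

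**5. What measuring everyone would give**

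*Assumed*: a fraction f = 0.2-0.5 do not reach the target and lose 3-5%; the rest are near 11.5%. The SD between the two groups is √(f(1 - f)) × (11.5 - loss).
- Smallest: √(0.2 × 0.8) × 6.5 = 2.60. With noise 20, r = 2.60/√(2.60² + 20²) = 0.13.
- Largest: √(0.5 × 0.5) × 8.5 = 4.25. With noise 10, r = 4.25/√(4.25² + 10²) = 0.39.
- By the formula in step 3, n for 80% power is about 49 at r = 0.39 and about 471 at r = 0.13. The analysis becomes informative, but not necessarily well powered.

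**The case against.** The strongest reply is that the study is about weight lost, not about being prescribed a programme. Measuring each person at a standard loss holds the exposure constant, and the within-person contrast of 0% against about 11.5% still bears on how weight affects pressure. That stands: the paired comparison is a valid description of people who reach the target.

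A reader might go further than the document allows in four ways.
- **That non-achievers are excluded by rule.** The text is silent about them. Their absence is inferred from there being no other measurement. Follow-up is also open-ended, so slow losers may qualify later, and no visit schedule is given from which to judge how often someone would pass 12% unmeasured.
- **That the reported mean is biased by a known amount.** With 20-50% non-achievers whose pressure changes by -3 to -5%, against -11.5% in achievers, the whole-cohort mean would be 0.8 × (-11.5) + 0.2 × (-5) = -10.2% to 0.5 × (-11.5) + 0.5 × (-3) = -7.3%. Every input except the window is assumed, and the plan nowhere claims that its mean applies to everyone prescribed the diet.
- **That the weight-pressure relation cannot be estimated at all.** The restriction affects the between-person analysis of WC%. Loss in kilograms still varies with baseline weight, although the plan does not define it as the change variable.
- **That the improve variable fails for the same reason.** It is undefined, so this cannot be asserted. Nor does the Spearman sentence name its pairs; WC% with PPC% or CoP change is the natural reading, not a stated one.

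It is also fair to object that pooling achievers and non-achievers mixes the amount lost with other differences between the groups. That stands and shapes the fix.

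**Conclusion.** The point holds in this form. The paired result describes those who reach 11-12% loss; it is valid for them and not shown to hold for all enrolled participants. The bound on the spread of WC% (SD about 0.29 if uniform, never above 0.50) follows from the plan's own window. The size of the resulting correlation rests on assumed values: about 0.01-0.03 for slope 1, noise SD 10-20 points and uniform spread, up to 0.05 at maximum spread, and at most 0.16 in the most favourable range-restriction case. In all of these a null Spearman result would say almost nothing about whether pressure depends on weight loss. The document supports no estimate of how many participants would miss the target, nor of any bias in the mean.

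**What to change.** **If measurement is still possible**
- Take the Session 2 weight and baropodometry in every enrolled participant, at the target or at a fixed maximum follow-up time counted from that participant's own Session 1, whichever comes first. The sponsor chooses the length. A single calendar closing date would give unequal follow-up under staggered enrolment. This concerns the timing of measurement only, not diet or exercise.
- Report the paired change in all participants with two sessions and, as a pre-stated set, in those with 11-12% loss.
- Report the numbers enrolled, reaching the target, and not re-measured, and compare the baseline data of these groups.
- Name the pairs to be related. Estimate the relation of weight change to pressure change in all measured participants, adjusted for baseline weight and baseline pressure. Label it observational, because most of the spread lies between achievers and non-achievers.

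**If measurement is already finished** (the document mixes past and conditional tenses, so this cannot be ruled out)
- State that the result is change among those reaching 11-12% loss.
- Report how many did not reach it.
- Drop the WC% correlation or state that it is uninformative.

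**Cost.** The first option needs one short visit per non-achiever and some protocol wording, and the whole-cohort mean change will probably be smaller than in achievers alone. The second needs wording and counts only.

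### Does the lack of a recorded walking speed undermine the dynamic plantar-pressure comparison between sessions?

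*Combined protocol and SAP*

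**What the plan says.** The Procedure section of the protocol sets the dynamic test as a barefoot walk at the participant's own speed, with landing on the third step: "participants would be asked to walk barefoot on the platform at their normal pace following the 3-step protocol". It then lists fluctuations to be kept small, pace among them, and gives the remedy: "imbalance and changes in gait speed) the procedure would be applied 3 times per session". The matching sentence for the standing test has the same form but leaves out gait speed: "fluctuations in static (as body weight oscillation and imbalance) the procedure would be applied 3 times per session". The same two clinicians assess each participant at both sessions.

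The outputs are named at the end of the Procedure section: "Peak pressures of these areas in kg/cm² and the position of the CoP, were obtained using the Footwork® software". The Equipment section adds weight and height. No walking speed, cadence, stance time or contact time is listed.

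Under Statistical Analysis, "Differences between Session 1 and Session 2, would be performed using mean comparison methods", meaning a paired t test or a Wilcoxon test with no covariates. Percentage changes in weight and pressure are correlated by Spearman's coefficient. A further variable has this stated purpose: "analyze the possible relationship between weight loss and the 9 pressure foot areas considered at Session 1". It covers the second visit too, in the standing and the walking test.

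**The concern.** Peak pressure under a walking foot may depend on how fast the person walks. The protocol itself treats pace as a source of fluctuation, and its Scientific Background says excess weight affects walking. Between the sessions participants lose 11-12% of body weight and also follow an exercise programme: "2 daily sessions of 15 minutes of anaerobic physical exercise depending on the capacity of the participants". Their natural pace could differ at Session 2 because they are lighter, because they have trained, or because they know the test. There is no control group.

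Three walks within a session do nothing about a shift that is common to all walks of that session. As nothing that records pace is listed, a reader of the dynamic results could not tell whether a pressure change came with a change of pace. If the report attributed the whole change to lower load on the foot, that attribution would be unsupported.

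**Working it through.** **Inputs.** From the Procedure section: 3 walks per session, 2 sessions, 9 foot areas, 2 modes (static and dynamic), both feet. The documents give no sample size, no SD, no pace data and no relation between pressure and speed. There is no planned figure to reproduce.

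**Step 1: what the three repeats do.** Let s be the walk-to-walk SD within a session. Assume the k walks of a session are averaged; the plan does not state the combining rule. The within-session error in one participant's session difference is then s × √(2/k).

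- k = 1: s × √2 = 1.414s
- k = 3: s × √(2/3) = 0.816s
- k = 10: s × √(2/10) = 0.447s

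A pressure shift D due to a different pace at Session 2 remains D for every k. The repeats therefore reduce variation within a session and leave a between-session shift untouched. Set side by side, the static and dynamic sentences have the same structure and both tie the repeats to the individual session. The natural reading is that the protocol means variation from one recording to the next. Against that target, three repeats are a proper measure.

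**Step 2: what is being estimated.** Write a participant's change in dynamic pressure as T = L + P, where L is the change that would occur at a fixed pace and P is the part that goes with a change of pace. The paired test estimates the mean of T. The Objective concerns the change in static and dynamic recordings as weight falls; it states no aim to estimate L alone. If lighter people walk differently, P is part of what happens when they lose weight. An unadjusted comparison at natural pace is the right analysis for T. Adjusting for pace would move away from T by taking out a possible consequence of the weight loss. The Spearman correlation of percentage changes likewise describes the total association.

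**Step 3: how much of the plan is touched.** 9 areas × 2 modes = 18 pressure outcomes, of which 9 are dynamic. With the feet kept separate, 18 × 2 = 36, of which 18 are dynamic. The dynamic centre of pressure could also be affected. The static outcomes are not.

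**Step 4: what a recorded pace would change.** It would need 3 × 2 = 6 contact times per participant, or 12 if each foot has its own three walks. The main comparison and its p-values would stay the same. The mean change in contact time would have a 95% confidence interval with half-width t(0.975, n−1)/√n in SDs of the paired change. For assumed sample sizes:

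- n = 20: 0.47
- n = 40: 0.32
- n = 60: 0.26

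An interval including zero would not prove equal pace. An interval excluding zero would not say whether weight loss, exercise or familiarity was the cause. A group mean near zero could also hide individual shifts that enter the correlation. In every case the correct wording of the dynamic result is the same: total change at natural pace.

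**The case for a change.** The strongest case on the other side is that the protocol names pace as a nuisance, guards against it only within a session, and then makes only between-session comparisons. An illustration gives this force. Take a pace-driven mean shift of 0.5 single-walk SDs, no direct effect of weight, three averaged walks, 30 participants, and a between-person SD of true change from 0.5 to 1.0. A two-sided test at 0.05 is then significant about 82% to 56% of the time. All these inputs are assumed.

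The arithmetic is right, but those rejections are false positives only if the claim under test is an effect of load at fixed pace. For the total change, which is what the plan compares, a shift that comes with weight loss is a true difference.

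Two parts of the objection stand. First, a shift due to exercise or familiarity is not an effect of weight loss. That follows from having no control group and from combining diet with exercise, and contact time would not resolve it. Second, as written, the plan gives a reader no information on pace. The platform recordings may contain contact time, but the documents do not say so. The formula for change in the centre of pressure contains an undefined time term; nothing shows it to be contact time, and the conclusion here does not rely on it.

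**Conclusion.** The concern does not hold as a fault in the plan. No pace measure is planned, and repeats cannot show a between-session shift; both observations are correct. Neither makes a planned result wrong. The dynamic comparison estimates the total before-after change at natural pace, which fits the stated Objective, and the three walks per session address the fluctuation the protocol names. What is left is a limit on explaining the mechanism, for 9 of 18 pressure outcomes (18 of 36 by foot) and possibly the dynamic centre of pressure. Its size and direction cannot be given from the documents.

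This rests on two readings: that the fluctuation sentence refers to variation within a session, and that the Objective asks for the total change. It would be different if the plan claimed an effect of reduced load at constant pace, which it does not. A contact-time summary or a sentence on limitations would be a reasonable extra, at the investigators' choice.

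### The only formal test of plantar pressure change is against zero change in kg/cm², so the plan does not show whether pressure fell more or less than the 11-12% weight loss built into the design

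*Combined protocol and SAP*

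**What the plan says.** The outcome is absolute. The end of the Procedure section gives it as "Peak pressures of these areas in kg/cm²", for 9 areas in static and dynamic recordings. The same section sets Session 2 at the point "when each participant lost between 11-12% of its corporal weight".

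Under Statistical Analysis, "Differences between Session 1 and Session 2, would be performed using mean comparison methods". The choice of method depends on a normality check: a paired Student's t-test if it is passed, a Wilcoxon test if not. Both are paired tests whose null is no change.

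The section also defines two relative changes, "Weight-Change % (WC%) = [(Weight at Session 2 – Weight at Session 1)/ Weight Session 1] x 100" and "Plantar-Pressure-Change % (PPC%) = [(Pressure at Session 2 – Pressure at Session 1)/ Pressure at Session 1] x 100". It analyses the change percentages by Spearman correlation and introduces a variable called *improve* to relate weight loss to the 9 areas, without defining it. The Procedure section adds a graph of pressure against each patient's two weights.

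Nothing divides pressure by body weight or tests PPC% against WC%. The Equipment section confirms that "weight and height were measured during each session", so the data for such a comparison exist.

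**The concern.** Zero change is not a neutral reference when the design itself lowers body weight by 11-12%. In quiet standing the total vertical load equals body weight, so some fall in absolute pressure is a reasonable expectation before any other effect is considered. A significant result shows that absolute pressure fell. It does not show whether the fall matched, exceeded or fell short of the weight loss.

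The converse matters too. An area with no absolute change would be reported as unaffected, although its pressure per kg of body weight had risen.

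The section does say that it will examine the relationship between weight loss and the 9 areas. The tools named for that are the Spearman correlation and the undefined *improve* variable. If neither can do the work, the plan cannot deliver an analysis that it announces.

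**Working it through.** **Inputs from the document.** Significance level 0.05 (sidedness not stated; two-sided assumed). Weight change -11% to -12%, midpoint -11.5%. Outcome in kg/cm². Paired t-test or Wilcoxon. The document gives no sample size, power, effect size or SD, so there is no planned figure to reproduce. Every n and SD below is an assumption.

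**1. What proportional scaling implies.** If P2/P1 = W2/W1, then PPC% = WC%. An example peak of 2.00 kg/cm² becomes 2.00 × 0.89 = 1.78 or 2.00 × 0.88 = 1.76.

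**2. How often the planned test is then significant.** Mean log change = ln(0.885) = -0.122. The noncentrality of the paired t-test is 0.122 × √n / SD, with n - 1 degrees of freedom. Power at two-sided 0.05:

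| SD of log change | n=20 | n=30 |
|---|---|---|
| 0.10 | 99.9% | 100% |
| 0.15 | 93% | 99% |
| 0.20 | 74% | 90% |
| 0.30 | 41% | 58% |

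On the percentage scale (mean PPC% of -11.5), the corresponding values at SD 15 are 90% and 98%, at SD 20 68% and 86%, and at SD 30 37% and 53%. The picture is the same.

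These figures are power to detect a real fall in absolute pressure. They are not false-positive rates. A test of P/W in the same scenario rejects at 5%, but only because proportionality was assumed, so that figure is no independent evidence.

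**3. An area with unchanged absolute pressure.** The ratio (P2/W2)/(P1/W1) equals 1/0.89 = 1.124 to 1/0.88 = 1.136. Peak pressure per kg is 12.4% to 13.6% higher. Equivalently, PPC% minus WC% is +11 to +12 points. The planned test would reject for this area only at its nominal 5%.

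**4. Can the Spearman correlation fill the gap?** I read it as PPC% against WC%. It tests rho = 0, which is a different hypothesis from PPC% = WC%. It also has almost no spread to work with. For WC% uniform on -12 to -11, its SD is 1/√12 = 0.289 points. With a true slope of 1 and a residual SD of 10 points, the Pearson correlation is 0.289/√(0.083 + 100) = 0.029; at 15 points it is 0.019, and at 20 points 0.014. Simulated Spearman rejection for n=20 to 100 and SD 10 to 20 is about 5-6%, barely above the significance level.

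If the 11-12% window were not kept and WC% ran uniformly from -20 to -3, power at n=20 would be 48%, 25% and 17% at SD 10, 15 and 20. The test would still not compare the two changes with each other.

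**5. The other planned items.** The *improve* variable has no definition or threshold. The graph carries no test. The CoP analysis addresses antero-posterior position, not the pressure change of a given area relative to weight.

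**The case against.** The strongest reply is that the objective is improvement brought about by decreasing body weight, so a fall caused by lower mass is an answer to the question asked. That stands. A reader might infer from the table that the planned test produces false positives in 41-100% of studies. It does not: absolute pressure really has fallen in that scenario, and detecting it is correct.

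A second reply is that PPC% and WC% are both planned, on one scale, and WC% is nearly constant, so anyone can set an area's mean PPC% beside -11 to -12. That also stands in part. The information is present. What is missing is an estimate with an interval for the difference, and a statement that this is the comparison to read.

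The third reply concerns mechanics. Peak pressure is local force per unit area, not an area's share of load. If contact area shrinks in proportion to weight, pressure is unchanged and load share is unchanged, yet P/W rises by about 13% (1/0.885). Walking pressure also depends on gait speed, which the Procedure section itself lists as a source of fluctuation. This stands in full. It is tempting to say that an area with unchanged pressure carries 13% more load per kg, that zero change must be false by mechanics alone, or that a change in P/W demonstrates redistribution. Data on peak pressure support none of these.

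**Conclusion.** The point holds in a limited form. The kg/cm² comparison is valid for the question whether absolute pressure fell. No planned test or interval addresses whether it fell more or less than body weight, and the one inferential link to weight has about 5-6% power under the design's own weight window, for assumed n=20-100 and SD 10-20 points.

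Under pure proportional scaling the planned test would be significant in about 41% to 100% of studies for assumed n=20-30 and SD of log change 0.10-0.30. An area with no absolute change would have peak pressure per kg 12-14% higher. The power figures depend on n and SD values that the protocol does not give. The 12-14% follows directly from the 11-12% weight loss.

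This is a gap in interpretation and does not invalidate the planned analysis.

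**What to change.** Keep the kg/cm² comparison as planned. Beside it, for each of the 9 areas and for static and dynamic recordings, report the paired difference PPC% minus WC% with a 95% CI. The log form ln(P2/W2) - ln(P1/W1) serves equally well; choose one in advance. Label it as the change relative to proportional scaling with body weight.

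State three rules in the Statistical Analysis section:

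- Proportional scaling is a benchmark and not an exact mechanical null, because contact area and gait speed may change between sessions.
- A pressure change beyond the weight loss is claimed only from this comparison.
- The comparison is not read as a change in load share or as redistribution.

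Define the *improve* variable or drop it, and do not rely on the Spearman result to relate pressure to weight within a one-point range.

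The cost is one derived variable and one extra column in the results tables. Both weights and both pressures are already collected, so no visit, measurement or participant is added.

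### Does averaging PPC% understate the fall in plantar pressure badly enough that another summary must be pre-specified?

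*Combined protocol and SAP*

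**What the plan says.** All of the relevant text except the measurement procedure is in the Statistical Analysis section.

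- **Purpose.** Percentage change is calculated "To quantify the difference between weight and plantar pressures and the CoP at Session 1 and Session 2". For pressure it is each participant's own ratio: "Plantar-Pressure-Change % (PPC%) = [(Pressure at Session 2 – Pressure at Session 1)/ Pressure at Session 1] x 100".
- **Named analysis.** The only analysis named for the percentage changes is that they "would be analyzed through Spearman correlation coefficient, according to normality".
- **Summary rule.** No summary is named for PPC%. The general descriptive rule, which follows "An initial exploratory analysis of all clinical variables would be carried out", is that "Continuous variables would be expressed as mean" with its SD.
- **Session comparison.** "Differences between Session 1 and Session 2, would be performed using mean comparison methods": paired t under normality, Wilcoxon otherwise.
- **Intervals.** The "confidence level set in the comparisons was 95" per cent, but no interval for the size of change is specified.

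The Procedure section states "Both feet would be subdivided into 9 areas: heel, midfoot, 5 MTHs, the Hallux, 2-5 toes", measured in static and dynamic conditions. It acknowledges that readings fluctuate within a person and schedules three trials per session, without saying how the three are combined.

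**The concern.** A ratio with a noisy denominator does not average to the true ratio. A participant whose Session 1 reading is low by chance gets an inflated P2/P1. One whose reading is high by chance gets a deflated ratio, but by less. If error is similar at both sessions and not fully shared between them, the mean of P2/P1 lies above the truth and mean PPC% shows too small a fall. A larger sample does not cure this; it narrows the interval around the wrong value.

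The objective is pressure improvement, and PPC% is the only percentage measure of pressure change that the plan defines. If repeatability differs between foot areas, areas with the same true fall would show different mean PPC%, which could be mistaken for a regional effect. The apparent remedy is to pre-specify another percentage summary with a 95% confidence interval.

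**Working it through.** **Inputs.** The plan states no sample size, SD, CV or reliability, so there is no planned figure to reproduce. From the documents: the PPC% formula, three trials per session, and the 11-12% weight loss that triggers Session 2. Assumed: pressure falls in proportion to weight (true ratio r = 0.885, a fall of 11.5%), session error CVs of 10-30%, and error correlation rho.

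**Bias with equal relative error.** For lognormal errors with mean 1 and the same CV c at both sessions, E[P2/P1] = r(1 + c²)^(1 - rho). For c = 0.20 and rho = 0.5: 0.885 × 1.04^0.5 = 0.9025, so mean PPC% is -9.75%.

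| Session CV | rho = 0.8 | rho = 0.5 | rho = 0 |
|---|---|---|---|
| 10% | -11.32 | -11.06 | -10.61 |
| 20% | -10.80 | -9.75 | -7.96 |
| 30% | -9.96 | -7.60 | -3.53 |

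**Three trials averaged, independent errors.** A per-trial CV of 20% gives a session CV of 0.20/√3 = 11.5% and a bias of about 0.885 × 0.04/3 = 1.2 points. Simulation with per-trial CV 10/20/30% gives mean PPC% of -11.21/-10.32/-8.85, an understatement of 0.3/1.2/2.6 points. At n = 20 (assumed) that is 0.18/0.36/0.54 of one standard error.

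**Where the direction fails.**
- Equal absolute errors: the bias is about c1²(r - rho), where c1 is the Session 1 CV. It is zero at rho = 0.885 and reverses above it. At c1 = 0.20 and rho = 0.95: 0.04 × (0.885 - 0.95) = -0.26 points.
- Unequal relative errors: E[P2/P1] = r·exp(s1² - rho·s1·s2), with s² = ln(1 + CV²). For CV 10% then 20%, s1² = 0.00995 and s1·s2 = 0.01976. Mean PPC% is then -11.49% at rho = 0.5 (no bias) and -12.02% at rho = 0.8 (fall overstated).

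**Do the replacements do better?** With equal noise and the same true change for everyone, yes. At n = 40, session CV 20/30% and rho = 0.5, a 95% t-interval on mean PPC% covers the true value 92/88% of the time. Intervals for the geometric mean ratio and the ratio of session means (Fieller) cover about 95%. Outside those conditions, no:
- Geometric mean ratio, unequal noise: r·exp((s1² - s2²)/2). For CV 10% then 20%, with s2² = 0.03922, this is 0.885 × exp(-0.01464) = 0.8721, or -12.79%, a 1.3-point error. At n = 40 and rho = 0.5 its interval covers 91.7%, against about 95% for mean PPC%. At rho = 0.8 the figures are 89.6% and 93.7%.
- Ratio of session means, when individual change varies: it differs from the mean individual change by (correlation of change with log baseline) × (SD of change) × (SD of log baseline). With correlation ±0.5, SD 0.10 and between-person CV 30% or 50% (log SD 0.294 or 0.472), that is ±1.5 or ±2.4 points. In simulation (n = 40, between-person CV 40%, session CV 10%, error correlation 0.5) Fieller intervals cover the mean individual change 89.6-90.4% of the time; mean PPC% covers it 94.7-94.9%.
- Geometric mean ratio, same spread of individual change: about 0.885 - 0.10²/(2 × 0.885) = 0.879, or -12.1%, which is 0.6 points below the mean individual change.

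**The case for a change.** The best argument for a change is that, read literally, the plan yields a mean PPC% as its only percentage effect size, that the mechanism is mathematical rather than speculative, and that a remedy costs a few lines. Two areas with the same true fall but session CVs of 10% and 30% (rho = 0.5) would read -11.1% and -7.6%. A reader can divide the reported session means, but cannot form a paired interval for that ratio without the between-session covariance.

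Much of this stands. The direction is right for equal relative errors that are not fully correlated, and the plan would be clearer if it named an effect size with an interval and said how the three trials are combined.

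It does not carry a change, for three reasons. First, mean PPC% as a headline result is an inference from a general descriptive rule; the plan's named use of the percentage changes is rank correlation, where a shift in the mean plays no part. Second, the comparison between sessions is made on paired readings. The paired t already targets the mean absolute change in kg/cm², for which a 95% interval comes with the test. Third, the large figures need a 30% session CV with uncorrelated errors, and nothing in the documents supports that over the milder cases.

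**Conclusion.** No change to the plan is needed. If PPC% is averaged, it can understate the fall: by 0.3 to 2.6 points when three independent trials with CV 10-30% are averaged, and by 0.4 to 3.9 points at session CV 10-30% with error correlation 0.5. The full range at equal CV runs from 0.2 points (CV 10%, rho = 0.8) to 8.0 (CV 30%, rho = 0). All of this assumes a true fall of 11.5% and equal relative errors; under other error structures the bias vanishes or reverses. The documents cannot show which case applies.

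The bias touches only a descriptive percentage. The session comparisons, taken to be made on the pressures themselves, and the Spearman analysis support the same conclusions with or without it. The replacements exchange one set of assumptions for another, and their own shifts of 0.6 to 2.4 points are of the same order as the bias they would remove. How PPC% is summarised, how the three trials are combined and which interval accompanies the change are missing details that an analyst can settle sensibly when reporting, for example by giving the mean absolute change with its 95% interval and saying which percentage summary is shown.
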